There is an increasing need for hospitals to do quality-assurance studies for in-patient PN to assess indications, PN prescription, complications, clinical outcomes and costs. The only in-patient population that is well studied is the intensive care unit (ICU) population. Several meta-analyses showed that PN was associated with higher infection rate, longer length of stay and higher mortality when compared with enteral nutrition (12,13). Results from these and other studies were the basis for the Canadian ICU Guidelines (13-17).

The aims of this study (already approved CAPCR 12/5174/AE) ) were to determine if PN prescribed in in-patients follows existing guidelines in terms of timing of nutrition support, prescription and monitoring and, whether it is associated with complications. In addition, clinical outcomes such as length of stay and mortality are assessed.

In addition, we will evaluate, in this cohort of patients, the effect of 2 different lipid emulsions, both approved by Health Canada (Intralipid based on soybean oil and ClinOleic based on olive oil). These lipid emulsions, readily available through our provider, will be prescribed alternatively according to standards of care. We also plan to do additional measurements relevant to nutrition which include: C-reactive protein [CRP], pre-albumin, subjective global assessment, hand grip strength and arm circumference at beginning and 10 days of PN (or at discontinuation if less than 10days). We will also monitor diagnoses of infections during PN, including 1 week after PN discontinuation if patients remain in hospital. We were advised to re-submit as a new study rather than as an amendment.

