## **Part B: Intralipid vs ClinOleic**

### **Primary Objective**

To evaluate metabolic, nutritional, infectious and inflammatory parameters in patients receiving SO-based lipid emulsion compared to those of patients receiving OO -based lipid emulsion.

- Primary Outcome: length of stay
- Secondary Outcomes: mortality, nutritional parameters (anthropometry, handgrip-strength, mid-arm circumference, , pre-albumin), inflammation (high sensitivity C-reactive protein; hs-CRP), documented infections, ICU stay, antibiotic-days, liver enzymes, essential fatty acid status

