### **Study design**

This is a prospective study that will evaluate the indications of parenteral nutrition in an inpatient setting. As part of their PN prescription, patients will receive either standard lipid (Intralipid) or OO-based lipid emulsion (ClinOleic), alternately depending on their time point of PN start, i.e. one person will receive Intralipid, the next one ClinOleic, etc. We will collect information from patients that have started with parenteral nutrition during their hospitalization and that are hospitalized in medical, surgical or ICU wards. We will also collect retrospective data of 100 patients to compare if the actions of the nutrition team and results change with respect to the prospective data.

Inclusion Criteria:

- Patients 18 years or older

- Patients that are expected to require PN for 5 days or more during their hospitalization
- Patients hospitalized in medical, surgical or ICU wards
- Signed informed consent either from the patient, their legally authorized representative or a direct family member

Exclusion Criteria:

- Patients without PN during their hospitalization

**Part A:** Patients will be approached when they start with PN during their hospitalization and will be followed until their last day of PN or, if occurred before PN ends, death. **Part**

**B:** For the proposed study, we will start PN as usual, according to the patients needs. We will randomly assign patients to receive either Intralipid or ClinOleic as the lipid emulsion in the PN. The amount of calories from the lipid emulsion will be equivalent.

Patients will be followed for one week after their last day on PN and, in addition, major outcomes such as mortality and length of stay will be assessed during the entire hospitalization.

Information regarding the patients nutrition will be obtained from the hospital chart and by direct communication with the PN team (dietitian, nurse, pharmacist) after signed informed consent.

We will analyze the nutritional indications and laboratory results of patients hospitalized in different units who are starting with PN alone or in combination with enteral or oral feeding twice a week. We will use a registry to enter the data.

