Measurements: :**Part A** 1) Patient demography: age, sex; 2) Type of patient: medical, surgical and/or ICU patients; 3) Type of any surgery the patient has during hospitalization; 4) Primary indications related to parenteral nutrition, comorbidities, updated CCI (31,32); 5) Nutritional assessment: weight, height, BMI, SGA, estimated energy and protein requirements; 6) comparison of energy received as a goal vs calculated energy requirements using published equations; 7) Energy, dextrose, aminoacids and lipids received by PN.

Total energy and proteins received including enteral nutrition and oral intake. Energy provided by Propofol, if received. In case of enteral nutrition, name and amount of product used; 8) Type of line used (peripheral or central); 9) Vascular access; 10) Reason for ending PN; 11) Number of times and reasons for interruption of PN; 12) Weekly PN related laboratory results; 13) Complications secondary to PN; 14) Outcome of patient

**Part B:** We will include the same measurements as in part A, but will add some additional nutritional parameters which will be done at baseline (Day 0) and after 10 days (Day 10)

with PN. Baseline or day 0 assessments to be done prior to or within 24 hours of PN initiation. Day 10 measurements to be done on day 10 of PN administration. If the PN ends before day 10, we will consider a cutoff at day 7 of PN. This means that if the PN ends before day 7, we will not repeat the measurements or blood work. If PN ends between days 7-9 we will repeat the measurements instead of doing them on day 10 for this special cases.

The parameters to measure will be: hand grip strength (kg), mid arm circumference (cm), SGA and weight as measures of nutritional status. We will also add hs-CRP, pre-albumin, and fatty acid profile in red blood cells (RBC) and plasma to the laboratory results at both time points. Clinical outcomes (documented infections, antibiotic-days or other adverse events) will be monitored for one week post-PN. In addition, mortality and length of stay will be documented for the entire hospitalization.

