## **Statistical analysis**

**Part A:** Descriptive statistics will be performed. Results will be expressed as absolute numbers and percentages, mean  $\pm$  standard deviation (SD) or median (minimum; maximum) depending on the variable types and distributions, separately for the prospective and the retrospective dataset.

For the prospective study, multivariate logistic regression will be performed to identify risk factors associated with specific PN prescription: for example, inadequate administration of PN. In addition, data from the prospective study and the retrospective chart review will be compared by unpaired t-test, Mann-Whitney-test or chi-square test as appropriate. A p value  $<0.05$  will be considered statistically significant. **Part**

**B:** For the Intralipid and the ClinOleic analysis, all variables will be tested for normal distribution (Shapiro Wilks test). *Primary outcome* is length of stay (in days). The Intralipid and ClinOleic groups will initially be compared with unpaired t-test or Mann-Whitney test as appropriate. *Secondary outcomes*: other clinical outcomes (days in ICU, antibiotic-days, infections, mortality) will also be analyzed the same way initially. For secondary outcomes that may change over time, i.e. hs-CRP, pre-albumin and other laboratory results, BMI, arm circumference, hand grip strength, changes will be compared between groups using unpaired t-test or Mann-Whitney test as appropriate. To account for possible covariate effects (eg. age, baseline BMI, Charlson comorbidity index), regression methods such as generalized linear models will be employed. All tests will be based on two-sided alternatives and a test will be considered statistically significant using alpha=0.05. SAS Enterprise Guide 4.1 software (SAS Institute Inc., Cary, NC, USA) will be used.

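### The Introduction and the Part B measurement rules disagree on reassessing patients whose PN ends before day 7, and the Statistical analysis section does not say whom the change comparisons cover

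*Combined protocol and SAP*

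**What the plan says.** The Introduction plans the added nutritional measurements (CRP, pre-albumin, SGA, hand grip strength, arm circumference) "at beginning and 10 days of PN (or at discontinuation if less than 10days". It sets no minimum duration of PN.

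The Part B paragraph of Measurements, under Study design, starts from the same day-0 and day-10 schedule and then adds a limit: "If the PN ends before day 10, we will consider a cutoff at day 7 of PN". It spells out the consequence: "if the PN ends before day 7, we will not repeat the measurements or blood work". PN that ends on days 7 to 9 triggers the repeat at that point. This paragraph also covers weight and the red-cell and plasma fatty acid profiles.

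The inclusion criteria admit "Patients that are expected to require PN for 5 days or more during their hospitalization".

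The Part B secondary outcomes include nutritional parameters (among them grip strength, mid-arm circumference and pre-albumin) and "inflammation (high sensitivity C-reactive protein; hs-CRP), documented infections, ICU stay, antibiotic-days, liver enzymes, essential fatty acid status".

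For outcomes that can change over time, the Statistical analysis section says that "changes will be compared between groups using unpaired t-test or Mann-Whitney test as appropriate". Regression is then mentioned: "To account for possible covariate effects (eg. age, baseline BMI, Charlson comorbidity index" are the covariates offered as examples. No analysis set is given for the change outcomes, and there is no rule for a patient without a second value.

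**The concern.** The two rules decide who has a second value, and therefore who can have a change score. A site following the Introduction would reassess a patient whose PN stopped on day 5 or 6; a site following Measurements would not.

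Under the Measurements rule, having a change score depends on how long PN lasted, which is determined after allocation. The between-group comparison then describes patients who were still on PN at day 7, not all patients allocated. That may be a sensible question to ask, but a reader of the results could not tell from the plan that it is the one being answered. At stake are the population and interpretation of several secondary outcomes, not the primary outcome.

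**Working it through.** The plan gives no figure on this point to reproduce, so the check is mainly a comparison of texts.

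**Step 1. The two rules side by side.**

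| When PN ends | Introduction | Measurements, Part B |
|---|---|---|
| Before day 7 | Reassess at discontinuation | Do not reassess |
| Days 7 to 9 | Reassess at discontinuation | Reassess then, in place of day 10 |
| Day 10 or later | Reassess on day 10 | Reassess on day 10 |

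The rules conflict in the first row only. Both are current text; neither is an amendment log, and nothing says that one overrides the other.

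**Step 2. Which measurements.** The conflict is certain for the five that the Introduction names. Its list is open-ended, so whether it also covers weight and fatty acids is unclear. Measurements applies its cutoff to all of them.

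**Step 3. Are such patients expected?** Yes. An expected course of 5 or 6 days meets the entry criterion and falls in the first row. The criterion concerns expected duration, so actual courses may be shorter still.

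**Step 4. What the analysis section needs.** A change needs two values. Measurements and Statistical analysis read together imply an analysis of patients with both values, hence of patients with at least 7 days of PN. That restriction is never stated.

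**Step 5. How many patients.** The documents do not give the share whose PN ends before day 7. With 150 per group (Feasibility and Sample Size) and an assumed share f, the number per group left without a second value under the Measurements rule is 150 × f:

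- f = 10%: 15 without, 135 left
- f = 30%: 45 without, 105 left
- f = 50%: 75 without, 75 left

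These are head counts under an assumption, not estimates. They also assume that everyone else is measured.

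**Step 6. The test on changes.** Let the outcome have the same SD σ at both assessments and correlation ρ between them. The variance of a change is 2σ²(1 − ρ). The residual variance of the follow-up value after regression on baseline is σ²(1 − ρ²). The ratio of the second to the first is (1 − ρ²) / [2(1 − ρ)] = (1 + ρ)/2, which is below 1 whenever ρ is below 1. So, apart from the one degree of freedom spent on baseline, the regression is more precise than the unadjusted comparison of changes, and it allows for chance baseline differences between groups. It uses a value already collected. It does not undo the selection by PN duration in Step 4.

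**Step 7. What is not affected.** Length of stay and mortality are documented for the whole hospitalization. Infections, antibiotic-days and ICU stay do not depend on the second assessment. The weekly PN laboratory results have their own schedule.

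**The case against.** The strongest reply is that Measurements is the operative text. It states the cutoff, draws out its consequence and deals with days 7 to 9 separately, so it reads as deliberate. The Introduction is a one-sentence summary, and one added clause there would remove the conflict. A minimum exposure before judging a lipid emulsion is also reasonable. Most of this stands: it makes the point minor, and it means the cutoff is not in itself a defect. It does not supply the missing analysis set.

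It can also be said that the covariates are only examples, so adjustment for the baseline outcome is not ruled out. True, but the stated initial comparison is unadjusted, and apart from baseline BMI the examples do not include the outcome's own baseline value.

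Three stronger readings are tempting, and the documents do not support them:

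- *That the day-7 cutoff biases the comparison, so the Introduction's rule is better.* The documents say nothing about PN duration by group or about the effect in patients who stop early. Those patients have received less lipid, so adding them could dilute a difference. Neither rule is always the less biased if duration differs between groups.
- *That planned power is lost.* The sample size rests on length of stay alone, and no marker has a target effect.
- *That reassessing early stoppers is free because "Patients will be followed for one week after their last day on PN".* Measurements describes that week as monitoring of clinical outcomes; it provides for no repeat bedside assessment or research sample.

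**Conclusion.** The inconsistency is real and confined to PN ending before day 7. It leaves unclear who contributes to the change comparisons for hs-CRP, pre-albumin, SGA, grip strength and arm circumference. If the Measurements rule governs, those results, and those for weight and fatty acids, apply only to patients with at least 7 days of PN, and the plan should say so.

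This conclusion rests on the text alone. How many patients are affected cannot be settled from the documents. Severity is minor, because only secondary outcomes are involved and the remedy is largely editorial. No bias and no loss of planned power is shown.

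**What to change.** 1. Reconcile the Introduction and the Part B Measurements paragraph so that a single rule applies, and make clear that it covers weight and fatty acids. Which rule is the sponsor's choice.
2. In Statistical analysis, Part B, state the analysis set for the change outcomes. If the day-7 cutoff stays, say that these results apply only to patients with at least 7 days of PN. Report for each group the number without a second value and the reason (PN ended early, death, discharge, other).
3. Make the main analysis of hs-CRP, pre-albumin, grip strength and arm circumference a regression of the follow-up value on group and the baseline value of that outcome, transformed if skewed, in place of the unadjusted t-test or Mann-Whitney test on changes.

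Cost: items 2 and 3 need a few sentences of text and no new baseline data; reasons for a missing second value must be recorded. Item 1 is a text correction if the cutoff is kept. If the Introduction's rule is chosen, each early stopper who can still be measured needs one more sample with its assays and one more bedside assessment, and the timing of the second value becomes more variable.

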#### **Part A:**

#### **Primary Objective**

- To evaluate parenteral nutrition prescriptions in hospitalized patients
- **Secondary Objectives**
- Describe patient population according to the pathology that caused the hospitalization
- Record the indication that determined the need for PN and whether they are medical, surgical or ICU patients
- Assess updated Charlson co-morbidity index (CCI)
- Record the number of days with intakes less than 50% of requirements or NPO before PN was prescribed
- Perform a nutritional assessment which includes: weight at admission (if recorded in chart) and at time of starting PN, height, body mass index (BMI), Subjective Global Assessment (SGA), albumin and estimate of nutritional requirements.
- Record the initial PN prescription in terms of energy and proteins
- Record how many days it took to reach the nutritional requirements estimated by the dietitian
- Compare energy received as a goal with calculated energy requirements using published equations
- Record the number of times PN was interrupted
- Record the total number of PN days the patient received
- Determine the type of line (central or peripheral) and number of days with peripheral and/or central lines.

- Determine the type of vascular access (if central line)
- Record laboratory results once a week to assess potential metabolic complications associated with PN
- Record catheter related infections, whether suspected or confirmed
- Record any other complications deemed related to PN
- Record number of antibiotic-days to treat catheter-associated infections
- Record the reason why PN was discontinued
- Record total length of stay
- Record in-hospital mortality and cause of mortality during PN as well as during entire hospital stay

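### Liver enzymes are a Part B outcome analysed as change, but they are not in the Day 0 and Day 10 blood work, so a pre-treatment baseline and a common interval are not assured

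*Combined protocol and SAP*

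**What the plan says.** **Outcome.** Under Part B: Intralipid vs ClinOleic, the secondary outcomes include "documented infections, ICU stay, antibiotic-days, liver enzymes, essential fatty acid status". This is the only place where the protocol names liver enzymes.

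**Timed assessments.** In Study design, the Part B measurements at Day 0 and after 10 days of PN are listed in two sentences. The physical measures come first: "The parameters to measure will be: hand grip strength (kg), mid arm circumference (cm), SGA and weight as measures of nutritional status". The blood tests follow: "We will also add hs-CRP, pre-albumin, and fatty acid profile in red blood cells (RBC) and plasma to the laboratory results at both time points". Liver enzymes are in neither. Day 0 assessments must be done no later than 24 hours after PN starts. The repeat is on day 10, or on days 7-9 if PN ends then, and is omitted if PN ends before day 7. The section on blood sample collection covers fatty acids, pre-albumin and hs-CRP only.

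**Routine laboratory record.** Part B also carries over the Part A items ("We will include the same measurements as in part A"), among them "12) Weekly PN related laboratory results". The Part A objectives say "Record laboratory results once a week to assess potential metabolic complications associated with PN". Neither gives the analytes or the PN day. A further sentence in Study design says that nutritional indications and laboratory results will be analysed for patients "who are starting with PN alone or in combination with enteral or oral feeding twice a week".

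**Analysis.** For outcomes that may change over time, the Part B analysis reads "hs-CRP, pre-albumin and other laboratory results, BMI, arm circumference, hand grip strength, changes will be compared between groups". It does not say which two values form a change.

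**The concern.** A change needs two values: one from before treatment, or close enough to its start to serve as a baseline, and one at a stated later time. For hs-CRP, pre-albumin and fatty acids the plan provides both. For liver enzymes it provides neither, and it does not say which enzymes are meant.

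Three things follow if the schedule stays as written:

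- A first value taken some days into PN is already on treatment. A change measured from it leaves out any effect that arose earlier, which dilutes the contrast between the lipids.
- Patients with a single value drop out of the comparison.
- Where a patient has several weekly values, the analyst must choose the pair after the data are in.

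A better analysis cannot repair this later, because a sample that was not drawn cannot be recovered. The outcome also has a stated motive: the Background gives possible hepatic effects of soybean oil emulsions as part of the reason to compare the two products, although it draws on children on long-term PN and on animal work and says that human data are lacking.

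**Working it through.** The plan gives no figure for liver enzyme sampling, missing values or PN duration, so there is nothing to reproduce. The check has two parts.

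**1. Text, side by side**

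| Item | hs-CRP, pre-albumin, fatty acids | Liver enzymes |
|---|---|---|
| Named as Part B outcome | yes | yes |
| Named at Day 0 and Day 10 (or 7-9) | yes | no |
| Sample described | yes | no |
| Baseline window | up to 24 hours after PN start | none stated |
| Stated source | timed study draw | weekly PN laboratory results, analytes not listed |
| Pair that forms the change | implied by the two time points | not defined |

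The Introduction's list of added measurements also omits liver enzymes. It omits fatty acids too, so it is not exhaustive and adds little.

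**2. What different laboratory calendars would give**

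These are illustrations under assumed timing. PN days are numbered from 0, L is the last PN day, and only draws during PN are counted.

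*(a) Weekly, anchored to PN start.* Draws fall on days 0, 7 and 14. Every patient has a baseline, every patient with L of 7 or more has a second value, and the first interval is always 7 days. No draw falls on Day 10 with the other markers.

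*(b) Weekly on a fixed weekday, PN starts spread evenly over the week.* The first draw falls on PN day u, with u = 0, 1, ..., 6 equally likely.

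- Draw on day 0 or 1: u is 0 or 1, so 2/7 = 29%.
- Two draws by day L: the number of u with u + 7 ≤ L, divided by 7. At L = 7 only u = 0 qualifies. At L = 10, u = 0, 1, 2 and 3 qualify.
- Draw on day 0 or 1 and another on day 7 or later: u = 0 needs L of at least 7, and u = 1 needs L of at least 8. The share is therefore 1/7 at L = 7 and 2/7 from L = 8.

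*(c) Two draws a week, 3 and 4 days apart, same even spread.* A draw falls on day 0 or 1 in 4/7 = 57%.

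| Last PN day L | 5 | 6 | 7 | 8 | 9 | 10 | 14 |
|---|---|---|---|---|---|---|---|
| (b) two draws during PN | 0/7 | 0/7 | 1/7 | 2/7 | 3/7 | 4/7 | 7/7 |
| (b) draw on day 0-1 and on day 7 or later | 0/7 | 0/7 | 1/7 | 2/7 | 2/7 | 2/7 | 2/7 |
| (c) two draws during PN | 5/7 | 7/7 | 7/7 | 7/7 | 7/7 | 7/7 | 7/7 |

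First-to-last intervals in (b) are 7 days up to L = 10, and 7 or 14 days at L = 14. In (c) they are 3-4 days at L = 5 or 6, 7-10 days at L = 10, and 10-14 days at L = 14.

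A chart value from before PN, if accepted as baseline, would raise the baseline shares in (b) and (c).

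**The case against.** The strongest reply is that the plan is only under-specified. The new assays are added to laboratory results at both time points, and study blood is taken at the routine ward draw. On that reading, routine results already exist on Day 0 and Day 10 and may include liver enzymes. This reading is open and cannot be excluded. But no section says that liver enzymes are part of those results, and a named outcome should not depend on that inference.

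Several stronger readings are tempting, and the documents do not support them:

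- *A reader might infer that many patients will lack a baseline or a second value.* The plan gives no laboratory calendar and no PN durations, and calendar (a) loses nobody with 7 or more days of PN. An inpatient may also have a chart value from before PN.
- *A reader might count only draws on Day 0 itself,* which gives 1/7 = 14% in (b). The protocol's own 24-hour window makes it 2/7 = 29%.
- *A reader might treat the whole loss as peculiar to liver enzymes.* It is not. If PN ends before day 7, the repeat is also omitted for hs-CRP and pre-albumin, and the day 7-9 rule varies their interval too. What is peculiar to liver enzymes is the missing baseline window and the missing planned repeat.
- *A reader might see weekly and twice weekly as a contradiction.* The twice-weekly sentence speaks of analysing results and plausibly describes review, so it needs clarifying.
- *A reader might infer bias between arms.* The documents give no reason why laboratory timing should differ by lipid.

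**Conclusion.** The concern holds in a limited form. Liver enzymes are a Part B outcome to be compared as change, yet the plan guarantees neither a pre-treatment value nor a common follow-up time, and it does not define the pair. The loss could be anything from none, with weekly tests anchored to PN start and at least 7 days of PN, to most patients, with fixed-weekday tests and short PN. Those end points rest on assumed calendars, on PN starts spread evenly over the week, and on leaving out values from before PN. With timing unrelated to arm, the cost is mainly lost precision and a diluted contrast in one secondary outcome. The primary outcome, length of stay, is not affected. The change is still worth making before recruitment, because it is cheap and undrawn samples cannot be recovered.

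**What to change.** - In Study design, Part B measurements: name the liver enzymes and add them to the Day 0 and Day 10 (or day 7-9) blood work, under the same 24-hour baseline window as hs-CRP and pre-albumin.
- In Statistical analysis, Part B: define the change in liver enzymes as the difference between those two values. Keep the weekly values for safety description.
- In Study design: state whether the twice-weekly sentence means review of results or sampling, and reconcile it with the weekly laboratory record.
- Bilirubin may be added to the panel. This is optional, since the stated outcome is liver enzymes.

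The cost is a routine panel on each of two draws that already take place, and only where the ward has not ordered it that day. No extra venepuncture is needed. Patients whose PN ends before day 7 will still have no repeat value, as for the other markers, and the interval will still be shorter for those measured on days 7-9.

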## **Feasibility and Sample Size**

**Part A:** Based on previous studies, there are about 200 in-patients per year receiving PN. All patients will be assessed as per standard medical guidelines for PN and it is expected that 90% will agree to participate in the project. We calculate that we will have enrolled about 50 patients for Part A, before we start with part B. We will later include 150 more patients from Part B to have a total of 200 patients. We will compare the data obtained with 100 retrospective patients to see if the actions of the nutrition team changed since we started the project.

**Part B:** When we receive the ClinOleic in the hospital, patients will receive either SO-based lipid emulsion (Intralipid= 150 patients) or OO-based lipid emulsion (ClinOleic=150 patients) on an alternate basis (one-to-one) for the duration of the PN.

The total number of patients including part A and part B is estimated to be 350 patients. It is expected to take about one and a half years to recruit this number of patients.

For the Intralipid and ClinOleic analysis, we based our sample size on a study that evaluated the use of either SO or SO + fish oil (FO) in 206 patients with gastrointestinal or colonic cancer during 7 days after surgery and found that the patients that were given the FO treatment had significantly shorter length of stay than the SO group (Mean (SD) 15(5) versus 17(8) p= 0.041). Also, they had fewer infectious complications (50). Another study compared soybean oil and soybean oil+FO in 57 elderly patients with colorectal cancer. In the treatment group, there were fewer infectious complications and incidences of systemic inflammatory response syndrome (SIRS), and shorter lengths of hospital stay were observed(51).

Based on this, we estimate that a sample size of 150 in each group with a power of 0.8 and alpha of 0.05 will be sufficient to show a similar difference in length of stay between the two groups (soybean or ClinOleic) using the online sample size calculation provided by G.W. Snedecor & W.G. Cochran  
<http://www.biomath.info/power/ttest.htm>.

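### Length of stay in Part B is not counted from PN start, so days before the lipid was assigned enter the primary comparison and cost power

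*Combined protocol and SAP*

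**What the plan says.** Length of stay is named as the Part B primary outcome under the Part B objectives and again in Statistical analysis, in days, with no start point. The only statements about the period are in Study design. The follow-up paragraph says that "major outcomes such as mortality and length of stay will be assessed during the entire hospitalization", and the Part B measurements end with "In addition, mortality and length of stay will be documented for the entire hospitalization". Part A, whose measurements Part B repeats, has the objective "Record total length of stay".

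Entry and assignment happen later than admission. On Part A entry the plan says: "Patients will be approached when they start with PN during their hospitalization". The lipid is given "alternately depending on their time point of PN start, i.e. one person will receive Intralipid, the next one ClinOleic, etc". Day 0 for the Part B measurements is also tied to PN initiation.

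The plan expects some time to pass before PN, since a Part A objective is: "Record the number of days with intakes less than 50% of requirements or NPO before PN was prescribed". That is not the same quantity as days from admission to PN start, which is not listed as a variable.

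Statistical analysis compares the arms by unpaired t-test or Mann-Whitney test. Regression adjustment follows, with age, baseline BMI and Charlson index as examples. Time before PN is not named.

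**The concern.** Days in hospital before PN are fixed by the time the lipid is assigned, so no lipid effect can reach them. If they are counted, each patient's outcome is the sum of a part that treatment may change and a part that it cannot. The second part brings variance and no signal. Patients come from medical, surgical and ICU wards, so the time from admission to PN probably varies a good deal.

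What is at stake is the power of the main comparison. The target difference is only 2 days. It is taken from a trial in cancer surgery patients treated for 7 days after the operation, and the sample size makes no allowance for variable time before PN. Days in ICU, a secondary outcome, has the same gap: no start is given, and some patients will already be in ICU when PN starts.

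**Working it through.** **Inputs from the documents.** Feasibility and Sample Size gives the planning figures "Mean (SD) 15(5) versus 17(8) p= 0.041", 150 per arm, power 0.8 and alpha 0.05. Statistical analysis makes tests two-sided. The difference is 17 − 15 = 2 days. The root-mean-square SD is √((5² + 8²)/2) = √44.5 = 6.67 days.

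**The plan's own figure.** With a 2-day difference and SD 6.67, a two-sided t-test needs 176 per arm for 80% power. With the simple mean SD of 6.5 it needs 167. A figure of 150 corresponds to a common SD of about 6.18, which the documents do not give. At 150 per arm and SD 6.67, power is 73.5%. This shortfall is a separate sample-size matter and is not caused by the start of the count. It matters here because it leaves no margin.

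**Assumptions.** (a) 6.67 is the SD of stay after PN start. (b) Stay before PN has SD s, for which the documents give no value, so a range is used. (c) The two parts are independent. Then

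SD of total stay = √(6.67² + s²),

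and power is that of the noncentral t-test with 150 per arm, a 2-day difference and two-sided alpha 0.05.

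| s (days, assumed) | SD of total stay | Power at 150 per arm | n per arm for 80% |
|---|---|---|---|
| 0 | 6.67 | 73.5% | 176 |
| 3 | 7.31 | 65.6% | 211 |
| 5 | 8.34 | 54.4% | 274 |
| 7 | 9.67 | 43.1% | 368 |
| 10 | 12.02 | 30.1% | 569 |

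**Relaxing independence.** With correlation r between the two parts, the variance is 44.5 + s² + 2·r·6.67·s. At s = 5, r = −0.2 gives SD 7.49 and power 63.5%; r = +0.4 gives SD 9.81 and power 42.1%.

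**Relaxing normality.** A simulation used gamma-distributed stays: mean 17 versus 15 days after PN start with SD 6.67, and an assumed mean of 8 days before PN. Mann-Whitney power was about 79% on stay after PN start. On total stay it was 57% at s = 5 and 42% at s = 10.

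**Type I error.** In the same simulation with no lipid effect and unbiased allocation, the rejection rate on total stay was 4.5% to 5.0%. Including the earlier days does not make the test invalid.

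**The case against.** **The start of the count is inferred.** The wording about the whole hospitalization follows a sentence that limits other follow-up to one week after PN, so it may say when observation ends and not when counting begins. This stands in part: the plan never states a start. But the Part A wording on total stay makes admission to discharge the natural reading, and on the other reading the primary outcome has an undefined origin, which the same edit cures.

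**The power figures rest on unseen inputs.** This stands. The SD before PN is assumed, and so is independence. The documents do not say whether the cited trial's stays run from admission or from surgery. If they run from admission, 6.67 already contains some pre-treatment variance, adding s² counts part of it twice, and the loss is smaller than tabulated.

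**Adjustment could deal with it, and total stay has its own interest.** The covariate list is open, so days before PN could be added. They are not prespecified, and the first test is unadjusted. Total stay is a recognisable resource outcome and can still be reported.

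**A stronger reading does not hold.** A reader might infer that a chance difference between arms in days before PN could pass for a lipid effect. At s = 7 that difference has standard error 7 × √(2/150) = 0.81 days, so imbalances of 1 day or more are not rare (about 22%). But this is ordinary sampling error, already inside the standard error of the test, 9.67 × √(2/150) = 1.12 days, and the type I error stays near 5%. Bias would need allocation that can be steered. The plan describes alternation and also speaks of random assignment; that is a separate issue.

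A reader might also extend the point to antibiotic-days. The documents give little support for that: Part A ties them to catheter-associated infections, and the Part B measurements monitor them until one week after PN.

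**Conclusion.** The point holds as a loss of power of unknown size. On the natural reading, the primary comparison includes days that precede assignment, and nothing in the plan removes them or prespecifies adjustment for them. If 6.67 days is the SD of stay after PN start and stay before PN is independent of it, power at 150 per arm goes from about 73% to between 66% and 30% as the pre-PN SD goes from 3 to 10 days. The direction does not depend on the exact SD chosen in that range, nor on the correlations tried at an SD of 5 days. The amount does, and it shrinks if 6.67 already covers pre-treatment days. The test stays valid under unbiased allocation, and an additive lipid effect on total stay is still estimated without bias. That makes this a should-fix: a cheap gain in precision on the main outcome, not a flaw that invalidates the comparison.

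**What to change.** In the Part B objectives, the Part B measurements and the Part B statistical analysis, define the primary outcome as days from Day 0 (assignment / PN initiation) to hospital discharge. Count days in ICU from Day 0 as well. Keep total stay from admission as a secondary or descriptive outcome. Report days from admission to Day 0 by arm as a baseline characteristic, and prespecify them as a covariate in any analysis of total stay.

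The cost is a wording change. The admission, PN start and discharge dates should be in the hospital chart, which is already a data source, and no patients or procedures are added. The one small downside is that stay from Day 0 compares less directly with published total stays, which is why total stay is still reported.
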